14.11 Missing Data and Sensitivity Analysis

The primary analysis will be based on the full analysis set with no imputation of missing data. Sensitivity analysis will be performed for both the primary effectiveness and safety endpoints using multiple imputations for missing data if the missing data percentage is greater than 5% (<https://pubmed.ncbi.nlm.nih.gov/29207961/>), as well as tipping-point analysis for the primary effectiveness endpoint to fully understand the missing data impact on the study results.

Medtronic Business Restricted

This document is electronically controlled

CONFIDENTIAL 056-F275 Rev E Clinical Investigation Plan Template

14.12 Multiplicity Adjustment

For the primary effectiveness endpoint only one hypothesis will be tested at alpha of 0.025 one-sided. For the primary safety endpoint (major complication rate), the closed test procedure (Holm's method) will be used to protect the overall study-wise error rate for surgery types (Nephrectomy, Prostatectomy and Cystectomy).

14.13 Minimization of Bias

Selection of subjects, treatment of subjects, and evaluation of study data are potential sources of bias. Methods incorporated in the study design to minimize potential bias include (but are not limited to):

- Potential for bias during this clinical investigation has been minimized by a well-controlled design, expected conduct under the terms of an approved clinical investigational plan and prospectively defined methods of data collection and analysis.
- All subjects meeting the study criteria will have all available data relevant to the study objectives collected per the investigational plan.
- Any known or foreseeable factors that comprise the outcomes of the clinical investigation or interpretation of results have been accounted for by the design of the clinical investigation.

In summary, potential sources of bias that may be encountered in this study have been considered and minimized by careful study design.

15. Ethics

15.1 Statement(s) of Compliance

This study will be conducted in compliance with international ethical and scientific quality standards, known as GCP. GCP includes review and approval by an independent IRB before initiating a study, continuing review of an ongoing study by an IRB, and obtaining and documenting the freely given informed consent of a subject before initiating the study.

The Expand URO study was designed to reflect GCP principles. These include the protection of the rights, safety and well-being of human subjects, controls to ensure the scientific conduct and credibility of the clinical investigation and the definition of responsibilities of the sponsor and Investigators. All Investigators shall avoid improper influence on or inducement of the subject, sponsor, monitor, other Investigator(s), or other parties participating in or contributing to the clinical investigation.

The principles of the DoH have been implemented through the IC process, IRB approval, study training, clinical trial registration, pre-clinical testing, risk-benefit assessment, and publication policy.

Ultimately, all study sites in all geographies will follow and comply with:

- Principles of DoH

Medtronic Business Restricted

This document is electronically controlled

CONFIDENTIAL 056-F275 Rev E Clinical Investigation Plan Template

Medtronic Expand URO Clinical Investigation Plan

MDT19051EINURO

Version 9.0

Page 82 of 111

Medtronic

- 21 CFR Part 11 (Electronic Records, Electronic Signatures)
- 21 CFR Part 54 (Financial Disclosure by Clinical Investigators)
- The CTA
- The procedures described within this CIP
- Local IRB Requirements

In addition to the regulatory requirements outlined above, the study will be conducted according to federal, national, and local laws, regulations, standards, and requirements of the countries/geographies where the study is being conducted. These include but are not limited to:

- In the United States, the study will be conducted under an FDA IDE in compliance with 21 CFR Parts:
 - 50: Protection of Human Subjects
 - 54: Financial Disclosure by Clinical Investigators
 - 56: IRBs
 - 812: IDEs

The study will be publicly registered in accordance with the 2007 FDAAA and DoH on <http://clinicaltrials.gov> (PL 110-85, section 810(a)). In addition, the study may be registered in local regulatory databases where required by local law.

Approval of the CIP and CIP amendments is required from the following groups prior to any study procedures at a study site:

- Medtronic
- Principal Investigators (where required by local law/regulations)
- Geography-specific regulatory authorities (if regulatory approval is required)
- An independent IRB.

Similarly, approval of subsequent revisions to the CIP is required at each study site from the above-mentioned groups prior to implementation of the revised CIP at the study site. Should an IRB or Regulatory Authority impose any additional requirements, they will be followed. If any action is taken by the IRB with respect to the investigation, that information is to be forwarded to Medtronic.

Pediatric, legally incompetent, or other vulnerable subjects are not eligible for the study. No insurance or compensation will be provided to study subjects.

Medtronic Business Restricted

This document is electronically controlled

CONFIDENTIAL 056-F275 Rev E Clinical Investigation Plan Template

16. Study Administration

16.1.1 Monitoring Visits

A site qualification visit may be conducted by Medtronic personnel (or designees) to review the clinical investigational plan and, regulatory and study requirements with the Investigator and study personnel.

Site initiation visits will be completed prior to enrollment of the first subject to ensure appropriate site staff are trained and delegated where applicable, and all required study documents are completed and collected.

Frequency of monitoring visits may be based upon subject enrollment, study compliance, number of adverse events, number of deviations, observations from previous monitoring visits and any suspected inconsistency in data that requires investigation. Regulatory documents will be reviewed at each study site. Monitoring for the study, including interim monitoring visits, and closeout visits, will be done in accordance with the study-specific monitoring plan. Monitoring visits may be conducted onsite or remotely.

Monitoring visits may be conducted periodically to assess study site progress, the Investigator's adherence to the CIP, regulatory compliance including but not limited to IRB approval and review of the study, maintenance of records and reports, and review of source documents against subject eCRFs in accordance with the study-specific monitoring plan. Monitors review study site regulatory and study compliance by identifying observations of non-compliance and communicating those observations along

Medtronic Business Restricted

This document is electronically controlled

CONFIDENTIAL 056-F275 Rev E Clinical Investigation Plan Template

with recommendations for preventative/corrective actions to study site personnel. Monitors may work with study personnel to determine appropriate corrective action recommendations and to identify trends within the study or at a particular study site.

16.2 Data Management

Data will be collected using an electronic data management system for the study. eCRF data will be stored in a secure, password-protected database which will be backed up nightly. Data will be reviewed using programmed and manual data checks. Data queries will be made available to study sites for resolution. Study management reports may be generated to monitor data quality and study progress. At the end of the study, the data will be frozen and will be retained indefinitely by Medtronic.

All records and other information about subjects participating in this study will be treated as confidential. Data will be transferred and processed by Medtronic, or a third party designated by Medtronic in a key coded form.

Procedures in the CIP require source documentation. Source documentation will be maintained at the study site. Source documents, which may include worksheets, subject medical records, programmer printouts, and interrogation files, must be created and maintained by the investigational study site team.

The Principal Investigator must ensure the accuracy, completeness, and timeliness of the recorded data and then provide his/her electronic signature on the appropriate eCRFs.

The Investigator's signature for specific eCRFs will be documented in compliance with local regulations. Changes to data previously submitted to the sponsor will require a new electronic signature by the Investigator to acknowledge/approve the changes.

16.3 Direct Access to Source Data/Documents

The Investigator(s)/institution(s) will permit inspection and study-related monitoring, audits, IRB review, and regulatory inspection(s), including direct access to original source data/documents per applicable laws and regulations.

16.4 Confidentiality

All information and data sent to parties involved in study conduct concerning subjects or their participation in this study will be considered confidential. Study sites will assign a unique SID to each subject. Records of the subject/SID relationship will be maintained by the study site. The SID number is to be recorded on all study documents to link them to the subject's medical records at the study site. Confidentiality of data will be observed by all parties involved at all times throughout the clinical investigation.

All data shall be secured against unauthorized access. The privacy of each subject and confidentiality of his/her information shall be preserved in reports and when publishing any data. In the US, "Protected Health Information" (PHI) will be maintained in compliance with the HIPAA of 1996. To maintain confidentiality, the subject's name or any other PHI should not be recorded on any study document other than the IC. This scenario will be covered in the IC. In the event a subject's name/PHI is included for any reason, it will be blinded as applicable. In the event of inability to blind the identification (e.g., digital media), it will be handled in a confidential manner by the authorized personnel. Data relating to the study might be made available to third parties (for example in case of an audit performed by RA), provided the data are treated as confidential and that the subject's privacy is guaranteed. No identifiable subject information will be published.

16.5 Liability/Warranty/Insurance Information

Medtronic maintains appropriate clinical study liability insurance coverage as required under applicable laws and regulations and will comply with applicable local law and custom concerning specific insurance coverage. If required, a clinical study insurance statement/certificate will be provided to the IRB.

16.6 CIP Amendments

Any revisions or amendments to the CIP or IC document, will be submitted to the FDA according to applicable regulations. Approval by the FDA and the site's IRB must be obtained prior to implementing a CIP revision at the study site.

16.7 Record Retention

The Principal Investigator will maintain the records of the study including all pertinent correspondence, the CIP with any/all amendments, all correspondence with and approval from the IRB, the clinical investigation agreement, the Investigator Agreement, individual subject records, and signed informed consent forms (ICFs).

The Principal Investigator is responsible for ensuring that all essential study documentation is retained and accessible for a minimum period of two years after the date the investigation is completed or terminated, or the records are no longer required to support a marketing application (or longer in compliance to local requirements). The retention period may be longer if required by Medtronic or local or global regulatory requirements. Medtronic will not store any personal data longer than necessary and always in line with the required storage periods defined by the applicable laws. Medtronic will delete or make any personal data anonymous after the applicable storage period has expired. The Principal Investigator will ensure that essential study documents are not destroyed until written permission has been obtained from Medtronic. Medtronic will be notified in writing prior to the transfer of study documentation.

16.8 Reporting Requirements

16.8.1 Investigator Reports

The Investigator is responsible for the preparation (review and signature) and submission to the sponsor of all case report forms, adverse events and adverse device effects (reported per the country-specific collection requirements), device deficiencies, deaths, and any deviations from the clinical investigation plan according to Table 13. If any action is taken by an IRB with respect to this study, copies of all pertinent documentation must be forwarded to Medtronic in a timely manner. Reports are subject to inspection and to the retention requirements as described above for Investigator records.

Safety data investigator reporting requirements are listed in Section 16.8.1. The investigator shall prepare and submit in a complete, accurate and timely manner the reports listed in this section.

Table 13. Investigator Reports Applicable to the United States per FDA Regulations

Report	Submit to	Description/Constraints
Withdrawal of IRB approval (either suspension or termination)	Sponsor and Relevant Authorities	The Investigator must report a withdrawal of approval by the reviewing IRB of the investigator's part of the investigation within 5 working days. (21 CFR 812.150(a)(2))
Progress report	Sponsor and IRB	The Investigator must submit this report to the sponsor and IRB at regular intervals, but in no event less than yearly intervals. (21 CFR 812.150 (a)(3)).
Study deviations	Sponsor and IRB	Notice of deviations from the CIP to protect the life or physical wellbeing of a subject in an emergency shall be given as soon as possible, but no later than 5 working days after the emergency occurred. Except in such emergency, prior approval is required for changes in the plan or deviations. If the deviation may affect the scientific soundness of the plan or the rights, safety and welfare of the subjects, the deviation must be approved by Medtronic, the IRB, and the FDA/applicable RA. If the deviation does not affect these issues, then only Medtronic must approve it. (21 CFR 812.150(a)(4))

Medtronic Expand URO Clinical Investigation Plan

MDT19051EINURO

Version 9.0

Page 87 of 111

Medtronic

Report	Submit to	Description/Constraints
Failure to obtain IC prior to investigational device use	Sponsor and IRBs	If an Investigator uses a device without obtaining IC, the Investigator shall report such use within 5 working days after device use. (21 CFR 812.150(a)(5))
Final report	Sponsor IRBs Relevant Authorities	This report must be submitted within 3 months of study completion or termination of the investigation or completion or termination of the Investigator's part of the investigation. (21 CFR 812.150(a)(6))
Other	IRB and FDA	An Investigator shall, upon request by a reviewing IRB, FDA or any other RA, provide accurate, complete, and current information about any aspect of the investigation. (21 CFR 812.150(a)(7))

16.9 Publication and Use of Information

- The Medtronic Publication and Authorship Policy is aligned with the International Committee of Medical Journal Editors (ICMJE) recommendations (www.icmje.org). The Sponsor will seek to publish, in appropriate peer-reviewed journals and scientific conferences, results of clinical studies where human subjects are involved. Publication will be pursued regardless of outcome, with the intent to communicate ROPI.
- information that will advance scientific and/or medical knowledge.
- While study results are owned by the Sponsor, all data on which a publication is based will be made available to all authors as required for their participation in the publication process. Furthermore, data may be published or used by study Investigators provided that such publication or use is in accordance with this protocol, the Medtronic Publication and Authorship Policy, and the Clinical Trial Agreement. Investigators must submit a copy of all manuscripts and/or abstracts to the Sponsor for review and comment at least 30 days prior to the planned submission. Medtronic acknowledges that its right to review and comment shall relate solely to the proprietary, licensing, and/or confidential rights Medtronic may have in such proposed publication, rather than whether such results and/or opinions are favorable to Medtronic.
- The publication of sub-studies, post-hoc analyses, regional results, or single-center experiences based on multicenter clinical studies should not precede that of the primary multicenter publication, and should cite the primary publication whenever possible, as required by specific journal and scientific meeting guidelines.

Medtronic Business Restricted

This document is electronically controlled

CONFIDENTIAL 056-F275 Rev E Clinical Investigation Plan Template

- Medtronic prohibits compensation for publication writing or editing activities to consultant health care providers (HCPs) (or to healthcare organizations) who serve as authors. Medtronic involvement in a publication (e.g., funding of the study; sponsor of the study; collection, analysis, and interpretation of data; professional writing assistance) must be disclosed according to journal-specific policies, submission requirements, and prevailing editorial standards, in addition to those specified by the ICMJE. Authors must ensure that an acknowledgement/disclosure statement is included in the body of the manuscript for Medtronic to review for accuracy. All authors must also disclose financial or personal affiliations that could be considered conflicts of interest as per journal/conference requirements.
- In compliance with independent ethical codes across the industry, Medtronic does not reimburse Investigators or healthcare providers for travel or registration to present Medtronic-sponsored clinical study data at third party scientific conferences.

16.9.1 Publication Committee

The study Steering Committee (**Section 6.5**) will also serve as the Publication Committee, in addition to appropriate members of the Medtronic medical and clinical departments (excluding marketing and sales). This committee will manage study publications with the goal of publishing findings from the data. The Publication Committee will develop the Publication Plan as a separate document.

The Publication Committee's role is to: (1) develop the Publication Plan under separate cover; (2) execute the Publication Plan; (3) oversee the publication of primary, secondary, and exploratory study results; (4) review and prioritize publication proposals; (5) provide input on publication content; and (6) apply and reinforce the authorship guidelines set forth in the Publication Plan. The committee will meet at regular intervals as needed.

The Publication Committee may use professional medical writers to assist in writing publications and/or presentations; however, all medical writing support must be appropriately disclosed according to the Medtronic Publication and Authorship Policy and journal/conference policies.

16.9.2 Criteria for Determining Authorship

- Publications will adhere to authorship criteria defined by the ICMJE. Individual authorship criteria defined by the target journal or conference will be followed when it differs from ICMJE criteria.
- All authors, including Medtronic personnel, must meet all four of the conditions below:
 1. Substantial contributions to conception and design of the work, or the acquisition, analysis, or interpretation of data for the work; AND
 2. Drafting the work or revising it critically for important intellectual content; AND

Medtronic Business Restricted

This document is electronically controlled

CONFIDENTIAL 056-F275 Rev E Clinical Investigation Plan Template

3. Final approval of the version to be published; AND
4. Agreement to be accountable for all aspects of the work in ensuring that questions related to the accuracy or integrity of any part of the work are appropriately investigated and resolved.
 - Study enrollment alone and membership in the Publication Committee do not guarantee authorship. Authorship on one publication does not guarantee authorship on any subsequent study publications.
 - Author selection strategy (based on ICMJE criteria) and potential authors will be discussed by the Publication Committee and included in the Publication Plan. Authorship will be evaluated on a continuous basis as writing and review progresses. Final authorship will be determined based on ICMJE contributions and must be reviewed by the Steering Committee prior to submission.

16.9.3 Transparency

Transparency of clinical study results will be maintained by the following means:

- A final report, describing the results of all objectives and analysis, will be distributed to all Investigators, IRBs, and RAs when required by local law
- Registering and posting the study results on clinicaltrials.gov based on the posting rules stipulated
- Submitting for publication the primary study results after the study ends
- Disclosing conflicts of interest (e.g., financial) of the coauthors of publications according to the policies set forth by the corresponding journals and conferences
- Making an individual study sites study data accessible to the corresponding Investigator after the completion of the study, if requested

16.10 Suspension or Early Termination

16.10.1 Planned Study Closure

- Study Closure is a process initiated by distribution of a study closure letter. Study closure is defined as closure of a study that occurs when Medtronic and/or regulatory requirements have been satisfied per the CIP and/or by a decision by Medtronic or RA, whichever occurs first. The study closure process is complete upon distribution of the Final Report or after final payments, whichever occurs last. Ongoing IRB oversight is required until the overall study closure process is complete. Refer to **Section 10.9** for additional information regarding study exit procedures.

16.10.2 Early Termination or Suspension

- Early Termination is the closure of a study that occurs prior to meeting defined endpoints. This is possible for the whole study or a single study site.
- Suspension is a temporary postponement of study activities related to enrollment and distribution of the product. This is possible for the whole study or a single study site.

16.10.2.1 Study-wide Termination or Suspension

Possible reasons for considering study-wide suspension or termination of the study include but are not limited to:

- AEs associated with the system or product under investigation which might endanger the safety or welfare of the subject
- Observed/suspected performance different from the product's design intent
- Decision by Medtronic or RA (where the study is operating under RA)
- Technical issues during the manufacturing process

Clavien-Dindo Grade IV complications will be continuously monitored by the sponsor for the safety and well-being of the subjects. Events reported as Clavien-Dindo Grade IV will be assessed by the Investigator and the sponsor as well as sent for adjudication by the independent CEC upon the sponsor's awareness date for the reported event.

Safety thresholds for Grade IV complication rates for the three study procedures are noted below:

- Cystectomy: 10%
- Nephrectomy: 8%
- Prostatectomy: 5%
- The above safety thresholds will be used by the sponsor to modify or stop the trial. The sponsor will review the Clavien-Dindo Grade IV complications for the first 30 subjects with 30-day data. A second review will be conducted for the second 30 subjects with 30-day data to ensure ongoing monitoring of subject safety.

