Complication	
Complications will be defined according to the Clavien-Dindo classification system.¹
 
Grade I: Any deviation from the normal postoperative course without the need for pharmacological treatment or surgical, endoscopic, and radiological interventions. Allowed therapeutic regimens are: drugs as antiemetics, antipyretics, analgetics, diuretics, electrolytes, and physiotherapy. This grade also includes wound infections opened at the bedside.
 
Grade II: Requiring pharmacological treatment with drugs other than such allowed for grade I complications. Blood transfusions and total parenteral nutrition are also included.
 
Grade III: Requiring surgical, endoscopic, or radiological intervention
 
Grade IIIa: Intervention not under general anesthesia
 
Grade IIIb: Intervention under general anesthesia
 
Grade IV: Life-threatening complication (including CNS complications)* requiring IC/ICU management
 
Grade IVa: Single organ dysfunction (including dialysis)
 
Grade IVb: Multiorgan dysfunction
 
Grade V: Death of a patient

Medtronic Business Restricted

This document is electronically controlled

CONFIDENTIAL 056-F275 Rev E Clinical Investigation Plan Template

	
NOTE 1: If the patient suffers from a complication at the time of discharge (see examples in Appendix 18.1), the suffix "d" (for "disability") is added to the respective grade of complication. This label indicates the need for a follow-up to fully evaluate the complication.
 
NOTE 2: *Brain hemorrhage, ischemic stroke, subarachnoidal bleeding, but excluding transient ischemic attacks. CNS, central nervous system; IC, intermediate care; ICU, intensive care unit.

Other	

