12.6 Subject Death

All subject deaths must be reported by the Investigator to Medtronic on an AE form (AE with a fatal outcome) as soon as possible after the Investigator first learns of the death. In case of death, there should be only one AE with the outcome of the event that led to death regardless of whether the death is related to the device system or procedure.

In the event that a subject's death is assessed as related to study procedure and/or study device, it is recommended that the Hugo™ RAS System or components are returned to Medtronic for analysis whenever possible per local process. Local laws and procedures must be followed where applicable. If any system component is returned to Medtronic, internal return product reporting systems may be used to gather additional information about the returned device/component.

A copy of the death certificate, if available and allowed by state/local law, should be sent to the Medtronic clinical study team. When a death occurs in a hospital, a copy of the death summary report and all relevant hospital records, if available should be sent to the Medtronic clinical study team. If an autopsy is conducted, a copy of the autopsy report should also be sent to the Medtronic clinical study team if available and allowed by state/local law. When the death occurs at a remote study site, it is the investigative study site's responsibility to attempt retrieval of information about the death. Additionally, device disposition information should be updated.

In summary, the following data will be collected:

- Date of death
- Detailed description of death
- Classification of death
- Relatedness to device and procedure
- Death disposition information

- Death summary/hospital records (if available and allowed by state/local law)
- Autopsy report (if available and allowed by state/local law)
- Death certificate (if available and allowed by state/local law)

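### The numeric stop/modify thresholds count only Clavien-Dindo Grade IV complications, so a death (Grade V) adds nothing to them, and the plan does not say how a Grade IV event that turns fatal is counted

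*Protocol*

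**What the plan says.** Protocol Section 16.10.2.1 is the only place in the available text of either document with numeric criteria for modifying or stopping the trial. It introduces them with "Safety thresholds for Grade IV complication rates for the three study procedures are noted below" and lists, in percent, "Cystectomy: 10", "Nephrectomy: 8" and "Prostatectomy: 5". Their role is explicit: "The above safety thresholds will be used by the sponsor to modify or stop the trial". The first look is described in the same terms: "The sponsor will review the Clavien-Dindo Grade IV complications for the first 30 subjects with 30-day data". A second review covers the next 30 subjects. The continuous monitoring announced just before the thresholds also names Grade IV alone.

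The complication scale in Section 12.4 (Table 7), repeated in the Glossary and Appendix 18.1, gives death its own grade: "Grade V: Death of a patient". Grade IV is a life-threatening complication needing intermediate or intensive care.

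On recording, Section 12.6 says that for a subject who dies "there should be only one AE with the outcome of the event that led to death". Section 12.3 has changes in the status of a reported event entered on its original form.

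The SAP plans no interim analysis (Section 7.8) and contains no stopping rule.

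**The concern.** A safety threshold should respond at least as strongly to a worse outcome as to a milder one. Here the counted class is a single grade with nothing above it. A subject who needs intensive care and survives adds one to the numerator; a subject who dies adds none. At either review the sponsor could correctly report every procedure below its limit although subjects had died.

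Two related gaps make the count less certain. The documents do not say whether a complication first reported as Grade IV is still counted if the subject later dies of it. They also do not say whether a subject who dies before day 30 belongs to the reviewed set, which is defined by having 30-day data; Section 10.9.1 lists death as a reason for study exit.

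**Working it through.** **Which grades are counted.** Could Grade IV be shorthand for Grade IV and above? Two places argue against it.

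- Where the protocol wants higher grades included, it says so. The primary safety endpoint (Sections 5.1.3 and 14.4.2) counts Grade III and above.
- Section 12.1, listing what the CEC adjudicates, names deaths separately from Grade III and IV complications.

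Nothing in the available text adds Grade V to the thresholds. The 30-day mortality goals in Section 14.5 do not fill the gap, because that section calls its goals benchmarks for interpretation.

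**What one event does to the rate.** The limits come with no derivation, error rate or event count, so there is no figure to reproduce. The following is an illustration.

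*Inputs from the documents:* limits of 10%, 8% and 5%; maximum cohorts of 31 cystectomies, 55 nephrectomies and 55 prostatectomies, 141 in total (Synopsis); reviews of 30 and a further 30 subjects.

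*Assumptions, not in the documents:* reviewed subjects split as 31:55:55, and a limit is crossed when the observed rate exceeds it.

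*Formulas:* subjects per procedure = review size × cohort / 141. Observed rate = subjects with a counted event / subjects reviewed in that procedure.

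First 30 subjects: 30 × 31/141 = 6.6 cystectomies, and 30 × 55/141 = 11.7 each for nephrectomy and prostatectomy.

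| Procedure | n | Limit | One survived Grade IV event | One death |
|---|---|---|---|---|
| Cystectomy | 6 to 7 | 10% | 1/6 = 16.7%, 1/7 = 14.3% | 0% |
| Nephrectomy | 11 to 12 | 8% | 1/11 = 9.1%, 1/12 = 8.3% | 0% |
| Prostatectomy | 11 to 12 | 5% | 1/11 = 9.1%, 1/12 = 8.3% | 0% |

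One counted event exceeds the limit in every procedure. Solving 1/n > limit shows how far this depends on the split: it holds for n up to 9 (cystectomy), 12 (nephrectomy) and 19 (prostatectomy).

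The text does not say whether the second review is cumulative. If it covers only the second 30, the table applies again. If it pools 60 subjects, the numbers are 60 × 31/141 = 13.2 and 60 × 55/141 = 23.4. Suppose one subject has a survived Grade IV event and another dies:

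| Procedure | n | Limit | Grade IV only (1 counted) | Grade IV or higher (2 counted) |
|---|---|---|---|---|
| Cystectomy | 13 to 14 | 10% | 7.7%, 7.1% | 15.4%, 14.3% |
| Nephrectomy | 23 to 24 | 8% | 4.3%, 4.2% | 8.7%, 8.3% |
| Prostatectomy | 23 to 24 | 5% | 4.3%, 4.2% | 8.7%, 8.3% |

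In each procedure, counting the death decides whether the limit is exceeded.

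**A Grade IV event that becomes fatal.** Section 12.6 allows only one event to carry the fatal outcome, and Section 12.3 updates the original form. Together they permit an intensive-care complication to end as one fatal event graded V. They do not require it. The examples of updates in Section 12.3 are actions taken, outcome and relatedness, not grade. Section 12.1 puts each event on its own form. Section 16.10.2.1 sends events to the CEC on the basis of the grade reported, which may precede the death. Loss from the count is possible but not established.

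**The case against.** The strongest reply is that deaths have a stricter route than a rate. They are collected whatever their cause (Section 12.1), reported promptly (Section 12.6) and all reviewed by the CEC (Section 12.6.1). The reasons for suspension in Section 16.10.2.1 are open-ended and include events that might endanger subjects, as well as any decision by the sponsor or a regulator. One death could halt the trial without any threshold. This stands: a reader might infer that the trial cannot respond to deaths, and the documents do not support that. However, these routes are discretionary, the CEC's stated task for deaths is relatedness, and none enters the numeric criterion.

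A reader might also infer that the monitored rate must fall when a Grade IV subject dies. That needs the grade to be overwritten, which no section prescribes.

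Nor is the rule in contradiction with the primary safety endpoint. A monitoring trigger and an endpoint may use different grades; leaving out the highest grade is a design choice that calls for a reason.

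Finally, the limits are labelled Grade IV rates and have no stated derivation, so they cannot be assumed to suit a wider definition. This also stands. Part of the oversight material (the content of Section 6.5 and the CEC Charter) is not in the available text, so the finding is limited to what can be read.

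**Conclusion.** The point holds for the numeric thresholds. As written, a death contributes zero to all three, while a less severe Grade IV complication contributes one. This follows from the text and needs no assumption. Its practical size does: with a proportional split and a limit crossed when exceeded, one survived Grade IV event among the first 30 subjects exceeds any limit (8.3% to 16.7%), and one death leaves the rate at 0%. With 60 subjects pooled, one Grade IV event plus one death in a procedure stays below its limit unless the death is counted.

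The fate of an event first reported as Grade IV that later proves fatal is an open question, not a demonstrated loss. Deaths are not unmonitored. The defect is that the one pre-specified numeric criterion in the available text omits them without explanation.

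**What to change.** Reconcile Sections 12.3, 12.4, 12.6 and 16.10.2.1 by defining the monitored rate in 16.10.2.1. It should state that:

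- the numerator is subjects with at least one complication of Grade IV or higher;
- an event first graded IV remains counted after a fatal outcome, with each subject counted once;
- subjects who die before day 30 belong to the reviewed set.

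The sponsor should confirm that its threshold values still apply to this definition, since their basis is not given; no value is proposed here. If the sponsor intends deaths to stay outside the thresholds, the section should say so and give the reason.

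The drafting cost is a sentence or two in a protocol amendment, and the data and CEC review of deaths already exist. The real cost is sensitivity. With about 6 to 12 subjects per procedure at the first review (under proportional enrolment), a single death could cross a limit and prompt sponsor review, possibly for a death unrelated to the device, since the thresholds carry no relatedness restriction. The CEC's relatedness finding would be available for that decision.
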